5.2.4 Minimal residual disease (MRD) determination

The level of minimum residual disease (MRD) will be assessed based on results from B-cell receptor (BCR) sequencing at timing of the radiological assessments. The level of MRD may conceptually be classified as “negative” (if MRD level is below a cut-off) or “positive” (if MRD level is above a cut-off). Three cut-offs may be used to classify the level of MRD: 10^{-4} , 10^{-5} , and 10^{-6} , where 10^{-5} is considered as the primary cut-off, and the others may be used for sensitivity analysis.

Given a cut-off, the “overall MRD status” is defined as:

- “MRD negative (cut-off)” as having at least one MRD negative result while on treatment (may or may not have indeterminate result)
- “MRD positive (cut-off)” as lacking an MRD negative result while on treatment (subjects who are continuously MRD positive, MRD indeterminant, not tested, or missing MRD samples throughout trial)

5.2.5 Responses to Prior Anti-Lymphoma Therapy

Subjects are considered **refractory** to a prior therapy if they exhibited no response after at least 2 cycles of therapy, or reappearance or growth of lymphoma after a duration of response of < 6 months.

Subjects are considered **relapsed** if they responded, then exhibited the reappearance or growth of lymphoma after at least 6 months duration of response.

5.3 Categorization of responses

Responses, as assessed by the investigator and Independent Review Committee (IRC; during the Dose Expansion part), will be categorized as follows, using the Lugano [2] or iwCLL [3] classification method. Further details are provided in Appendices 7, 8, 9 and 10 of the protocol (version 4.0).

The date of response (or progression) will be taken to be the initial date where the response (or progression) was identified. That date will be used for all calculations of duration of response, progression-free survival, etc.

In cases where the response is confirmed, the date of response (or progression) will be taken to be the initial date where the response (or progression) was identified. That date will be used for all calculations of duration of response, progression-free survival, etc.

Lugano or iwCLL Result	Complete Response	Overall Response	Disease Control Status
Complete Response or Complete Remission (CR)	Responder	Responder	In Disease Control
Partial Response or Partial Remission (PR), including nodular PR (nPR)	Non-Responder	Responder	In Disease Control
Stable Disease (SD) or No Response	Non-Responder	Non-Responder	In Disease Control
Progressive Disease (PD)	Non-Responder	Non-Responder	Not In Disease Control
Not Evaluable (NE)	Non-Responder	Non-Responder	Not In Disease Control
Missing response	Non-Responder	Non-Responder	Not In Disease Control

5.3.1 Complete Response or Remission

5.3.1.1 *Complete Response per Lugano criteria, for B-cell NHL excluding CLL*

Subjects meeting CR criteria based on FDG-PET CT (or CT/MRI and FDG-PET when PET CT not available) per the Lugano criteria will be recorded as CR on the CRF.

Those with documented bone marrow involvement at Screening will require a confirmatory bone marrow aspirate and/or biopsy within 30 days, as described in Table 9.1 of the protocol, within 30 days of the initial documentation of CR. If the bone marrow sample shows bone marrow involvement, the initial response of CR will be retroactively changed to PR.

Subjects without documented bone marrow involvement at Screening will not require further confirmation of their classification as complete responder.

5.3.1.2 *Complete Remission per iwCLL criteria, for CLL*

In order to meet CR criteria per the iwCLL, subjects must have a normocellular bone marrow sample, with no CLL cells or B-lymphoid nodules, as described in Appendix 8.

5.3.2 Partial Response

5.3.2.1 *Partial Response per Lugano criteria, for B-cell NHL excluding CLL*

Subjects achieving partial response per Lugano criteria, whether an initial assessment of PR or an unconfirmed CR which is later changed to PR on the basis of bone marrow involvement, do not require any further confirmation.

5.3.2.2 *Partial Remission per iwCLL criteria, for CLL*

Subjects achieving partial response per iwCLL criteria must meet improvement criteria as specified in Appendix 8 of the protocol. Nodal partial remission (nPR) is defined as subjects in remission with residual nodules or suspicious lymphocytic infiltrates in a bone marrow biopsy which often indicates a residual disease.

Subjects achieving a partial remission per iwCLL criteria may not require a bone marrow assessment if sufficient information on the hematopoietic system is available to determine partial remission.

5.3.3 Progressive Disease

Progressive disease must be confirmed by 2 consecutive scans, at least 4 weeks apart, as described in protocol 9.2.3.2.

5.4 *Calculation of durations and times to events*

Duration of an event occurring on or after first dose date, in days, is calculated as event end date – event start date + 1.

Durations in weeks will be calculated as durations in days divided by 7.

Durations in months will be calculated as durations in days divided by 30.4375.

Time from initial diagnosis will be calculated in months, from the initial diagnosis of the primary site to the first dose date: (first dose date – date of first diagnosis) /30.4375

Time from last anti-CD20 therapy to treatment with GEN3009 will be calculated in months, from the latest treatment end date of any agent administered as part of the last prior anti-lymphoma treatment that included an anti-CD20 compound to the first dose date: (first dose date – date of last anti-CD20 therapy +1) /30.4375

Total number of months on trial will be calculated as: (last contact date – first dose date + 1)/30.4375

Follow-up time will be calculated, in weeks, as: (date of last disease assessment by investigator – first dose date + 1) / 7.

Total treatment duration will be calculated in days as:

- If last cycle is Cycle 1, 2 or 3: last dose date – first dose date + 7
- If last cycle is Cycle 4 – 9: last dose date – first dose date + 14
- If last cycle is Cycle 10 or later: last dose date – first dose date + 28

Progression-free survival (PFS)

PFS is defined as the time in days from Day 1 of Cycle 1 to the day (+1) of first documented disease progression, or the day (+1) of death due to any cause, whichever comes first. Progression does not require confirmation (per Lugano criteria). PFS censoring will be based on Table C1 in Appendix C in the FDA Guidance for Industry: Clinical Trial Endpoints for the Approval of Non-small Cell Lung Cancer Drugs and Biologics [4].

Duration of response (DOR) will be calculated in days as:

DOR = date of first documented progressive disease or death from any cause – date of first response + 1.

In the absence of progressive disease or death, responders will be censored per the FDA censoring rule utilized for PFS, as presented in Appendix I. First response is defined as first documented occurrence of CR or PR (including any complete responses pending confirmation). DOR will only be calculated for those subjects achieving CR or PR.

Overall survival (OS) will be calculated in days as:

OS = date of death from any cause – date of first dose of investigational treatment + 1

Subjects not known to have died will be censored at the last date known to be alive.

Time to next anti-lymphoma treatment (TTNT) will be calculated in days as:

TTNT = date of first recorded administration of subsequent anti-lymphoma therapy – date of first dose of investigational treatment + 1

In the absence of recorded subsequent anti-lymphoma therapy, subjects will be censored at the last non-missing disease assessment.

Time to response (TTR) will be calculated in days as:

TTR = date of first response – date of first dose of GEN3009 + 1

TTR will only be calculated for those subjects achieving CR or PR.

Sustained MRD negative response will be calculated as described in Section 10.2.8.

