11.8.2 Duration of Response

DoR only applies to subjects whose best objective response is CR or PR and is defined as the number of days from the first documentation of objective tumor response (CR or PR) to the date of first PD or death.

DoR will be censored and summarized in the same way as PFS (section [11.8.4](#)). The detailed censoring rules are specified in the SAP.

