FAS	Full analysis set
FDA	US Food & Drug Administration
FL	Follicular Lymphoma

HGBCL	High Grade B-cell Lymphoma
ICH	International Conference on Harmonization
IRC	Independent Review Committee
LLOQ	Lower Limit of Quantification
MedDRA	Medical Dictionary for Regulatory Activities
MRD	Minimal Residual Disease
MTD	Maximum Tolerated Dose
MZL	Marginal Zone Lymphoma
nPR	nodal Partial Remission
NE	Not Estimable
ORR	Overall Response Rate
OS	Overall Survival
PAS	Pharmacokinetic Analysis Set
PD	Progressive Disease
PK	Pharmacokinetics
PMBCL	Primary mediastinal B-cell Lymphoma
PR	Partial Response or Partial Remission
PT	Preferred Term
QTcF	Fridericia's correction to the QT interval
R/R	Relapsed or Refractory
RP2D	Recommend Phase 2 Dose
SAE	Serious Adverse Event
SAF	Safety analysis set
SAP	Statistical Analysis Plan
SD	Stable Disease
SFE	Secure File Exchange
SLL	Small Lymphocytic Lymphoma
SOC	System Organ Class
$t_{1/2}$	Terminal phase half-life
TEAE	Treatment Emergent Adverse Event
TLF	Tables, Listings, and Figures
T_{max}	Time of maximum observed concentration
TTNT	Time to Next Anti-Lymphoma Therapy
TTR	Time To Response
WHODRUG	World Health Organization Drug Dictionary

19 References

1. Standard Country or Area Codes for Statistical Use provided by the Statistics Division of the United Nations Secretariat (<http://unstats.un.org/unsd/methods/m49/m49regin.htm>)
4. U.S. Food and Drug Administration. *Clinical Trial Endpoints for the Approval of Non-Small Cell Lung Cancer Drugs and Biologics Guidance for Industry*. Apr 2015. <https://www.fda.gov/media/116860/download>

20 Appendices

Appendix I: Progression and Censoring Criteria for Analyses of Progression-Free Survival and Duration of Response

These censoring rules will be applied to PFS and DoR, as per Section 5.4.

Situation	Date of Progression or Censoring	Censoring Rule
Incomplete or no baseline tumor assessments	Cycle 1 Day 1 (in lieu of randomization)	Censored

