Progression documented between scheduled visits	Earliest of: - Date progression assessment showing new lesion (if progression is based on new lesion) - Date of last progression assessment	Progressed
No progression	Date of last progression assessment with no documented progression	Censored
Treatment discontinuation for undocumented progression	Date of last progression assessment with no documented progression	Censored
Treatment discontinuation for toxicity or other reason	Date of last progression assessment with no documented progression	Censored
Next anti-lymphoma treatment started	Date of last progression assessment with documented non-progression before start of new treatment	Censored
Death before first PD assessment	Date of death	Progressed
Death between adequate assessment visits	Date of death	Progressed
Death or progression after more than one missed visit	Date of last progression assessment with documented non-progression	Censored

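### SAP 5.3.3 demands two-scan confirmation of every progression while SAP 5.4 waives it for PFS, citing only Lugano; the event rule for DoR and for CLL is left unclear

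*SAP*

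**What the plan says.** SAP 5.3.3 sets a general rule: "Progressive disease must be confirmed by 2 consecutive scans, at least 4 weeks apart, as described in protocol 9.2.3.2". SAP 5.3.1 and 5.3.2 each have separate Lugano and iwCLL parts; 5.3.3 has none.

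SAP 5.4 defines PFS by the first documented progression or death and adds: "Progression does not require confirmation (per Lugano criteria"). For duration of response it gives "DOR = date of first documented progressive disease or death from any cause – date of first response + 1", then "In the absence of progressive disease or death, responders will be censored per the FDA censoring rule utilized for PFS". It does not mention confirmation for DoR.

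SAP 5.3 dates a response or progression to its first identification and says: "That date will be used for all calculations of duration of response, progression-free survival, etc". SAP Appendix I heads its single censoring table: "These censoring rules will be applied to PFS and DoR, as per Section 5.4". Protocol 11.8.2 says: "DoR will be censored and summarized in the same way as PFS". Protocol 11.8.4 defines PFS to the first documented progression or death for all subjects, with no confirmation condition.

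The current protocol 9.2.3.2 deals with possible pseudo-progression in enlarging nodes, to be settled by later imaging or biopsy. It contains no two-scan rule and no four-week interval. The SAP is based on protocol v4.0 (Amendment 2); the protocol available is Amendment 5, v7.0.

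SAP 10.2.1 and 10.2.3 refer the reader to Section 5.3.1 for the censoring rule. Section 5.3.1 defines complete response.

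**The concern.** Sections 5.3.3 and 5.4 stand next to each other and give opposite instructions. Section 5.3.3 cannot be set aside as guidance on continuing treatment, because it belongs to the response-categorization section whose dates feed both PFS and DoR.

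The conflict matters for a subject who shows progression once and never has a second scan, for example because new therapy starts first. One programmer would count an event; another, following 5.3.3, would censor. If PFS follows 5.4 and DoR follows 5.3.3, the same subject has a PFS event and a censored DoR. Censoring valid progression lengthens both endpoints. Exposure is largest for DoR, which rests on few subjects, and for CLL, where valid progression may not appear on a scan.

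**Working it through.** **1. Which rule applies where.**

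| Endpoint | Text favouring no confirmation | Text favouring confirmation |
|---|---|---|
| PFS, Lugano cohorts | SAP 5.4 waiver; protocol 11.8.4 | SAP 5.3.3 |
| DoR, all cohorts | first-documented wording; SAP 5.3 dating paragraph; shared Appendix I; protocol 11.8.2 | SAP 5.3.3 |
| PFS, CLL | protocol 11.8.4; first-documented wording in SAP 5.4 | SAP 5.3.3; the waiver cites only Lugano |

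Appendix I has no row for unconfirmed progression, so it does not decide the matter.

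**2. CLL criteria.** In protocol Appendix 8 a single Group A or Group B criterion is enough for progression, and constitutional symptoms alone do not count. That leaves 6 parameters. Scans can show 2 (nodes; liver or spleen). They cannot show 4 (lymphocyte count, platelets, hemoglobin, marrow). This counts criteria; it is not the share of CLL progressions, which the documents do not give.

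**3. Worked subject.** Response at Week 6, progression at Week 12, new therapy before another scan.
- No confirmation needed: PFS event at Week 12; DoR = 6 × 7 + 1 = 43 days, event.
- 5.3.3 taken literally: the Appendix I new-treatment row applies, "Date of last progression assessment with documented non-progression before start of new treatment". PFS is censored at Week 6; DoR = 0 + 1 = 1 day, censored.

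If a second scan does confirm progression, SAP 5.3 dates it back to the first scan and the two readings agree.

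**4. Opportunity for a second scan.** Scheduled scans are at Weeks 6, 12, 18, 24, 36 and 48, then every 24 weeks (protocol 9.2.2.1). The gaps after a first progression scan are 6, 6, 6, 12, 12 and then 24 weeks, unless an extra scan is done.

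**5. Illustrative size.** The plan states no figure to reproduce: PFS and DoR have no sample-size or event target. Assumptions: exponential times, progression seen at the next scheduled scan, and k progressions (up to Week 48) recoded as censored at the previous scan, or at the response date for DoR. The medians, response week and k are assumed. The shift is the recoded Kaplan-Meier estimate minus the original.

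PFS, 20 subjects, Week 24 (sampling SD about 10 to 11 points):

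| Median PFS | Base | k = 1 | k = 2 |
|---|---|---|---|
| 12 weeks | 25.0% | +1.6 | +3.3 |
| 20 weeks | 43.8% | +2.0 | +4.2 |
| 30 weeks | 57.4% | +2.3 | +4.6 |

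If the one subject dies 4 to 8 weeks later without new therapy and death counts as the event, the PFS shift is 0.6 to 1.4 points.

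DoR at 6 months (26.1 weeks), 7 responders: 0.35 × 20, using the CLL response rate that protocol 2.3.1 quotes for another CD37 antibody (sampling SD about 16 to 19 points):

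| Median DoR | Response Week 6: k = 1 / 2 | Response Week 12: k = 1 / 2 |
|---|---|---|
| 12 weeks | +4.9 / +11.1 | +4.6 / +10.6 |
| 20 weeks | +5.8 / +12.6 | +6.7 / +14.9 |
| 30 weeks | +6.1 / +13.0 | +7.7 / +16.7 |

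With death as the event and k = 1, the DoR shift is 0.0 (response at Week 6) to 4.8 points (response at Week 12). With 14 responders (0.69 × 20 = 13.8, from the higher rate quoted in the same section), the shifts are 2.3 to 3.8 for k = 1 and 4.8 to 8.0 for k = 2. With k = 0 nothing changes.

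A second illustration leaves a fixed share of all progressions unconfirmed in a 20-subject cohort. At shares of 10% or 25%, the typical median PFS estimate moves from 12 to 18 weeks when the true median is 12, and does not move when it is 26 or 52.

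**The case against.** The best defence is that the plan is clearer than 5.3.3 alone suggests. The specific PFS sentence overrides the general one. DoR shares the first-documented wording, the dating paragraph and the censoring table, and protocol 11.8.2 ties it to PFS. Protocol 11.8.4 sets no confirmation condition for any disease, CLL included. This stands to a large extent: a reader might infer that DoR has no event rule at all, and the documents do not support that. What DoR lacks is a confirmation rule of its own, and a mandatory sentence in 5.3.3 still points the other way.

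A second defence is that 5.3.3 applies as described in protocol 9.2.3.2, and the v4.0 text behind that reference is not available. It may have confined the rule to possible pseudo-progression, and reading it to require a repeat scan for falling platelets gives an absurd result. This also stands as a caution. It would be wrong to infer that the SAP misreported the protocol it was written from; one can say only that the reference does not match the current 9.2.3.2. As printed, 5.3.3 carries no such limit.

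Third, protocol 9.2.2.1 continues imaging to confirmation of progression and allows extra scans, so cases may be few. However, protocol 9.2.3.1 stops imaging at progression, both sections stop it at new therapy, and the continued-imaging note in protocol 8.1 is not attached to progression by response criteria. Such cases are foreseeable; their number is unknown.

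**Conclusion.** The contradiction is real and should be resolved before analysis. For PFS under Lugano it is mostly a matter of tidying, because 5.4 most naturally governs. For DoR the intended rule can be inferred but is not secured. For CLL the SAP waiver does not clearly apply, and a literal two-scan rule cannot confirm four of the six parameters that can define progression.

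A reader might conclude that PFS and DoR are materially biased as planned. The documents do not support that. Bias arises only if 5.3.3 is followed and only through progression never confirmed on a second scan, and no rate of that is given. Its direction would be toward longer PFS and DoR. Every Kaplan-Meier shift computed for one or two such subjects is below one sampling SD and rests on assumed medians, response weeks and counts. Both endpoints are secondary and descriptive, with no hypothesis test; the primary ORR and DLT endpoints are not materially affected. The wrong 5.3.1 pointers are a separate, plain error. This is a change that should be made, not one on which the trial's main conclusions depend.

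**What to change.** Replace SAP 5.3.3 with one endpoint rule for PFS and DoR:

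- The event is the first documented progression under the applicable criteria (Lugano or iwCLL), dated at the first assessment showing it, or death. No separate two-scan confirmation is required.
- The rule applies to the investigator assessment (main analysis) and in the same way to any IRC-based sensitivity analysis.
- An assessment not designated progression because of possible pseudo-progression under the current protocol 9.2.3.2 is not an event unless progression is later established; it is then dated to the first such assessment.
- For CLL, protocol Appendix 8 is followed, with a statement that the marrow check in protocol 9.2.2.2 applies to single-parameter cytopenic progression.

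Update the 9.2.3.2 reference to the current protocol version, and redirect the 5.3.1 pointers in SAP 10.2.1 and 10.2.3 to Section 5.4 and Appendix I. A line in Appendix I limiting the discontinuation rows to subjects without documented progression or death is optional, since SAP 5.4, 10.2.1 and 10.2.3 already say so.

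The cost is SAP wording only, with no new data or analyses. PFS and DoR may look slightly shorter than under a literal 5.3.3. One gap remains: a subject with suspected pseudo-progression who starts new therapy before re-assessment is still censored, and that depends on the assessor's judgement.

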9.2.2 Evaluations

Efficacy assessments will be conducted as specified in the visit assessment schedules (refer to [Table 2](#), [Table 3](#), [Table 5](#), [Table 6](#), [Table 10](#), and [Table 11](#) will include the following: imaging assessments (including hepatic involvement and splenic involvement [size by vertical: cranial to caudal]), bone marrow assessment (as applicable), physical exam including constitutional symptoms, ECOG performance status, MRD status, and other procedures as necessary. All efficacy assessments should be conducted throughout the trial until disease progression, the start of new anti-cancer therapy, death or withdrawal of consent from trial participation, whichever occurs first.

Response assessment for B-cell NHL will be according to revised response criteria ([Cheson et al., 2014](#)) (refer to [Appendix 7](#)) and for CLL according to the iwCLL ([Hallek et al., 2018](#)) (refer to [Appendix 8](#)).

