9.3.6 Survival Status

Survival status will be assessed every 3 months via telephone contact, email, or on-site visit, after the last administration of GEN3009 and/or GEN3013 and will continue until the subject dies or withdraws from the trial. Data will be collected as reported by the subject regarding disease status, new anti-lymphoma treatment, any other malignancy other than the disease under study (ie, a second primary malignancy), and survival status, if available. If the subject is not available for this assessment, the response should be entered as “lost to follow up” ([Section 8.4](#)).

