10.2.6 Time to next anti-lymphoma therapy

TTNT will be derived for all subjects receiving trial treatment. The number of subjects treated, as well as the numbers subsequently undergoing a non-trial anti-lymphoma therapy and those censored without undergoing another anti-lymphoma therapy, will be presented by cohort.

TTNT will be summarized, analysed, and presented graphically as described for DOR.

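### SAP 5.4 counts next therapies recorded after the last disease assessment but discards therapy-free time known from the same follow-up, so Kaplan-Meier TTNT (death not an event) runs short

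*SAP*

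**What the plan says.** SAP 5.4 defines the endpoint as "TTNT = date of first recorded administration of subsequent anti-lymphoma therapy – date of first dose of investigational treatment + 1". It sets no limit on how long after the last disease assessment a therapy may start and still count. The censoring rule is "In the absence of recorded subsequent anti-lymphoma therapy, subjects will be censored at the last non-missing disease assessment". Death is not mentioned, so a subject who dies without new therapy is also censored at the last assessment.

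SAP 10.2.6 sets the population ("TTNT will be derived for all subjects receiving trial treatment") and the method ("TTNT will be summarized, analysed, and presented graphically as described for DOR"). The method for DOR is Kaplan-Meier, and no competing-risk method is named.

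The protocol sets two different observation windows:

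- **Disease assessments (9.2.2):** "All efficacy assessments should be conducted throughout the trial until disease progression, the start of new anti-cancer therapy", or death or withdrawal of consent.
- **Survival follow-up (9.3.6):** contact every 3 months until death or withdrawal. "Data will be collected as reported by the subject regarding disease status, new anti-lymphoma treatment", among other items. The visit schedules (Tables 3, 6 and 11) place these contacts every 12 weeks after the last dose.

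Two neighbouring definitions in SAP 5.4 differ from the TTNT rule. For overall survival, "Subjects not known to have died will be censored at the last date known to be alive". For duration of response death is an event: "DOR = date of first documented progressive disease or death from any cause".

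**The concern.** Censoring at the last disease assessment suits PFS and DOR, because progression is found at those assessments. A new therapy is not. It is learned at survival contacts that continue after assessments have stopped.

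Take two subjects who progress at the same scan and are followed by the same contacts. One starts a new therapy four months later and stays in the risk set until that date. The other is known to be untreated four months later but is removed back at the scan. Whether a subject stays in the risk set after progression thus depends on whether the event later happens. The risk sets lose subjects known to be event-free, each later event removes too large a share of the curve, and TTNT looks shorter than it is.

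At stake is the credibility of one descriptive secondary endpoint, by cohort of up to 20 subjects. No test or decision rule uses it.

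**Working it through.** The documents give no median, event count or rate for TTNT, so there is no planned figure to reproduce. The rule was checked in three ways.

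**1. Ten-subject example (invented data).** New therapies start at months 5, 7, 9 and 11. Six subjects have no new therapy; their last assessments are at months 2, 3, 4, 4, 6 and 8, and contact continues to month 12. With n the number at risk, S is multiplied by (1 − 1/n) at each event.

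- SAP rule: n = 6, 4, 2, 1. S = 5/6 = 0.833; × 3/4 = 0.625; × 1/2 = 0.312; × 0 = 0. Median 9 months.
- Censoring at last contact: n = 10, 9, 8, 7. S = 0.90, 0.80, 0.70, 0.60. Median not reached, which agrees with 6 of 10 known to be untreated at month 12.
- If two of the six die untreated at months 6 and 10, S at month 11 is 0.9 × 7/8 × 6/7 × 4/5 = 0.54 with censoring at death, and 0.40 with death as an event.

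**2. Simulation with the protocol's calendar.** From protocol 9.2.2.1: scans at weeks 6, 12, 18, 24, 36, 48, then every 24 weeks. Scans stop at detected progression (PD), and 12-weekly contacts follow. Assumed, not in the documents: median survival before PD of 60 months, and every input in the first three columns below. There were 400,000 subjects per row; times are in months.

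| Median PD / mean gap to therapy / median post-PD survival | Never treated | Follow-up | Median, SAP rule | Median, last contact | Median, therapy or death | 12-month therapy-free, SAP vs last contact | Difference (points) |
|---|---|---|---|---|---|---|---|
| 4 / 1 / 8 | 0% | 12-24 | 5.87 | 5.95 | 5.42 | 0.172 vs 0.198 | 2.6 |
| 4 / 3 / 8 | 0% | 12-24 | 8.47 | 8.81 | 6.86 | 0.278 vs 0.326 | 4.8 |
| 6 / 2 / 12 | 0% | 12-24 | 9.46 | 9.71 | 8.46 | 0.359 vs 0.391 | 3.2 |
| 12 / 2 / 18 | 0% | 12-24 | 16.43 | 16.95 | 12.75 | 0.587 vs 0.612 | 2.5 |
| 12 / 3 / 18 | 0% | 6-18 | 12.24 | 15.89 | 13.68 | 0.523 vs 0.610 | 8.7 |
| 4 / 3 / 4 | 0% | 12-24 | 8.80 | 9.40 | 6.41 | 0.310 vs 0.373 | 6.3 |
| 18 / 2 / 24 | 0% | 18-36 | 22.24 | 22.83 | 17.46 | 0.717 vs 0.722 | 0.5 |
| 4 / 2 / 12 | 20% | 12-24 | 8.42 | 9.35 | 7.50 | 0.278 vs 0.392 | 11.4 |
| 6 / 2 / 18 | 20% | 12-24 | 11.08 | 12.06 | 9.79 | 0.420 vs 0.502 | 8.2 |
| 12 / 2 / 24 | 20% | 12-24 | 16.92 | 19.58 | 16.68 | 0.642 vs 0.685 | 4.3 |
| 4 / 2 / 12 | 40% | 12-24 | 9.52 | 13.96 | 9.11 | 0.359 vs 0.540 | 18.1 |
| 6 / 2 / 18 | 40% | 12-24 | 12.03 | 18.04 | 12.00 | 0.502 vs 0.623 | 12.1 |
| 12 / 2 / 24 | 40% | 12-24 | 17.64 | 22.33 | 18.67 | 0.711 vs 0.762 | 5.1 |

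The SAP-rule median is below the last-contact median in all 13 rows, from 1% short (5.87 vs 5.95) to 33% short (12.03 vs 18.04). Against complete follow-up, the last-contact rule is itself 0 to 0.7 points low at 12 months in twelve rows, and 4.5 points low (0.610 vs 0.655) in the row with 6-18 months of follow-up.

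In 3,000 simulated cohorts of 20 under each of rows 2, 3 and 4, the SAP-rule median lay below the complete-follow-up median in 42%, 24% and 50% of cohorts, and above it in none.

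**3. High never-treated fraction and short survival.** Assumed: median PD 4 months, therapy a mean of 1.5 months later, 18 months of follow-up, PD detected without delay. The 12-month percentage with new therapy is:

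| Intending therapy / median post-PD survival | SAP rule | Last contact | Cumulative incidence |
|---|---|---|---|
| 50% / 4 months | 56 | 42 | 33 |
| 70% / 6 months | 70 | 58 | 50 |

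The censoring date accounts for 56 − 42 = 14 and 70 − 58 = 12 points. The remaining 9 and 8 points come from moving to cumulative incidence. With the protocol's scan weeks the censoring-date effect is 52.8 − 39.7 = 13.1 and 65.5 − 54.6 = 10.9 points.

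**The case against.** The strongest reply concerns direction and scope.

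- **Direction depends on how death is treated.** If the target is therapy or death, the SAP rule usually errs the other way. The composite median is below the SAP-rule median in 11 of the 13 rows (for example 6.86 vs 8.47). In the two scenarios of step 3, therapy or death by 12 months is about 73% and 74%, against 56% and 70% under the SAP rule. This stands: a short bias can be claimed only for TTNT with death not an event.
- **A reader might take 56% against 33% as the size of the error.** That gap mixes the censoring date with a change of estimand. Only the 14 points belong to the rule.
- **A reader might infer that leaving deaths out is itself a mistake.** The documents do not support that. Whether death is an event, a competing event or a censoring event is a choice of definition. What can be faulted is that the choice is not stated and that untreated deaths are dated back to the last assessment.
- **A reader might assume high early mortality throughout.** The 3 to 4 month life expectancy in protocol 2.1.1.1 concerns R/R DLBCL not responding to second-line immunochemotherapy. For early-relapsing FL, protocol 2.1.1.2 gives 34-50% alive at 5 years, and nothing comparable is shown for CLL. With indolent-type assumptions (median PD 6-12 months, 90-95% intending therapy, post-progression survival 12-36 months) the effect at 12 months is about 1 to 3 points (41.5 vs 40.1%; 65.5 vs 62.1%).
- **Assessments do not always end at first progression.** Protocol 9.2.2.1 continues imaging to confirmation of progression, 9.2.3.2 allows for pseudo-progression, and SAP 5.3.3 asks for two scans at least 4 weeks apart. This narrows the lost window for some subjects but does not close it.

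**Conclusion.** The mismatch is in the text and the rule gives a biased estimate. For TTNT with death not an event, the direction was short in every scenario tried. The size is not fixed by the documents: about 0.5 to 18 points on the 12-month probability of new therapy, against last-contact censoring. It was 0.5 to 3.2 points where everyone goes on to therapy after a mean gap of 1-2 months. It was about 12 to 14 points where 30-50% never intend further therapy and median post-progression survival is 4-6 months. All of these rest on assumed progression, treatment and survival rates.

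The handling of death is a separate, open estimand choice, not an error. Consequence is low. TTNT is descriptive, no hypothesis is tested, and it is absent from the current protocol's endpoint tables (Tables 17 to 20) and from protocol 11.8.

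**What to change.** In SAP 5.4, replace the TTNT censoring date with the last contact on which the subject was known not to have started new anti-lymphoma therapy. If death is not an event, censor untreated deaths at death.

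Separately, state in advance whether death without new therapy is a competing event, reported as cumulative incidence, or an event. If it is an event, rename the endpoint to say so.

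SAP 9.2 points to 10.2.5 (overall survival) for the TTNT summary, while TTNT is in 10.2.6; correct this pointer at the same time.

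The cost is a few sentences. The contacts are already scheduled and SAP 5.4 already uses a last contact date. One caution is that protocol 9.3.6 takes this information as reported by the subject and where available, so each contact should record explicitly that no new therapy has started. The SAP was written to protocol version 4.0 and the current protocol is version 7.0, so the change can go into the update that the SAP needs anyway.
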